Due to known drug interactions, patients taking the following medications will be excluded. Nortriptyline: monoamine oxidase inhibitors (MAO) such as phenelzine. Patients on oral contraceptives will be asked to use a secondary method as nortriptyline can reduce the effectiveness of oral contraceptives.

Topiramate: acetazolamide (kidney stones), digoxin

An electronic health record (EPIC) will be used for secure collection of all patient data. Questionnaires filled out by patients will be scanned into EPIC.

A sample size of 100, which nets 90 subjects into the randomized medication trial (two equal groups of 45 subjects each), yields a power of 82% to detect a difference in patient-reported effectiveness/acceptability between the nortriptyline and topiramate groups after two months of medication use. This sample size estimate assumes 60% of subjects using nortriptyline report it as effective/acceptable, in contrast to half as many subjects (or 30%) using topiramate. The power calculation is based on a two-sized Z-test with pooled variance and targeted significance level (alpha) of 0.05. The expected difference in outcome between the two groups is based on our prior research ([name], 2012).

Adverse effects of the two drugs will be assessed. Specifically, the following known side effects will be asked about and recorded.

Nortriptyline: somnolence, weight gain, dry mouth, blurred vision

Topiramate: Weight loss, parasthesias, forgetfulness, nausea, diarrhea, fatigue

The subjects will be allowed to maintain therapy or taper off the drugs. It is anticipated that those that derive benefit from the drugs will choose to stay on them. All patients will have the option of remaining under our care outside of the study.

c) If the proposed study is a clinical trial where a drug, vaccine, device or other treatment is compared to a placebo group or comparison treatment group, what are the guidelines or endpoints by which early decisions regarding efficacy or lack of efficacy can be made? For example, it may be reasonable to stop enrollment on a study when efficacy has already been clearly demonstrated, to avoid unnecessary enrollments of additional subjects. Alternatively, it may be reasonable to stop enrollment when it is clear that efficacy will never be demonstrated, given the statistical power of the study as designed. Describe the guidelines that are in place to assist in making these determinations, if relevant to the proposed study.

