*** Risks ***

9. Risks

There is no research that can be considered totally risk free (e.g., a potential risk of breach of confidentiality). Therefore, when describing the risk, the lowest level of risk is "no more than minimal risk".

Page numbers from a sponsor's protocol/grant may be referenced in 9.1, 9.2, 9.3, and 9.4.

1. Use of investigational devices. Please include the clinical adverse events (AEs) associated with each of the devices with an indication of frequency, severity and reversibility. This information can often be found in the Investigator(s) brochure. NOTE: Include any likely adverse effects associated with procedures that subjects may experience while in the study.
2. Use of investigational drugs. Please include the clinical AEs associated with each of the drugs with an indication of frequency, severity and reversibility. This information can often be found in the Investigator(s) brochure. NOTE: Include any likely adverse effects associated with placebos or washout periods that subjects may experience while in the study.
3. Use of FDA approved drugs, reagents, chemicals, or biologic products. Please include the clinical AEs associated with each of the drugs with an indication of frequency, severity and reversibility. This information can often be found in the package insert provided by the manufacturer. NOTE: Include any likely adverse effects associated with placebos or washout periods that subjects may experience while in the study.

Nortriptyline: Possible adverse reactions

Cardiovascular - Hypotension, hypertension, tachycardia, palpitation, myocardial infarction,

Protocol Title: A Prospective randomized cross-over trial of nortriptyline and topiramate in the initial treatment of vestibular migraine

arrhythmias,
heart block, stroke.

Psychiatric - Confusional states (especially in the elderly) with hallucinations, disorientation, delusions; anxiety, restlessness, agitation; insomnia, panic, nightmares; hypomania; exacerbation of psychosis.

Neurologic - Numbness, tingling, paresthesias of extremities; incoordination, ataxia, tremors; peripheral neuropathy; extrapyramidal symptoms; seizures, alteration in EEG patterns; tinnitus.

Anticholinergic - Dry mouth and, rarely, associated sublingual adenitis; blurred vision, disturbance of accommodation, mydriasis; constipation, paralytic ileus; urinary retention, delayed micturition, dilation of the urinary tract.

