Allergic - Skin rash, petechiae, urticaria, itching, photosensitization (avoid excessive exposure to sunlight); edema (general or of face and tongue), drug fever, cross-sensitivity with other tricyclic drugs.

Hematologic - Bone marrow depression, including agranulocytosis; eosinophilia; purpura; thrombocytopenia.

Gastrointestinal - Nausea and vomiting, anorexia, epigastric distress, diarrhea, peculiar taste, stomatitis, abdominal cramps, black-tongue.

Endocrine - Gynecomastia in the male, breast enlargement and galactorrhea in the female; increased or decreased libido, impotence; testicular swelling; elevation or depression of blood sugar levels; syndrome of inappropriate ADH (antidiuretic hormone) secretion.

Other - Jaundice (simulating obstructive), altered liver function; weight gain or loss; perspiration; Suicide

Serotonin Syndrome (>>>>)

Topiramate: Possible adverse reactions

oral contraceptive pills may have reduced efficacy when used with topiramate

paresthesia (35-50%) and taste perversion (10-15%)

Acute Myopia and Secondary Angle Closure Glaucoma, Visual Field Defects, Oligohidrosis and Hyperthermia, Metabolic Acidosis, Suicidal Behavior and Ideation, Cognitive/Neuropsychiatric Adverse Reactions (including cognitive dysfunction, psychiatric/behavioral disturbances and somnolence/fatigue), Hyperammonemia and Encephalopathy, Kidney Stones. Additionally, the adverse effects section in the package insert Table 10 (incidence of 2-5%) includes fatigue, hypoesthesia, language problems, nausea, diarrhea, decreased weight, arthralgia anorexia, somnolence, difficulty with memory, difficulty with concentration/attention.

Patients will be asked to wean off of drug over the course of one week if they have been on the drug more than a week. Specific issues we will watch for include:

Nortriptyline: At the low dosages used in this study, abrupt withdrawal has not been shown to be harmful.

Topiramate: Acute myopia due to secondary angle closure glaucoma has been rarely reported in acute withdrawal.

4. Use of FDA approved devices. Please include the clinical adverse events (AEs) associated with each of the devices with an indication of frequency, severity and reversibility. This information can often be found in the Investigator(s) brochure. NOTE: Include any likely adverse effects associated with procedures that subjects may experience while in the study.

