If no, please justify why not.

Treatment is standard of care

b. Is there a Data Safety Monitoring Plan (DSMP)? N

Protocol Title: A Prospective randomized cross-over trial of nortriptyline and topiramate in the initial treatment of vestibular migraine

Note, if all relevant plan information is included in DSMB question above, select 'Yes' and state "see above" in the answer box.

If yes, provide details (labeled a-e) including: a) what types of data or events are captured and how are they documented, b) who is monitoring data, their independence/affiliation with the research and their degrees/qualifications, c) frequency of aggregate data review, d) who is reviewing SAEs in real time (MD or DO), and e) stopping/halting rules (if any exist).

If no, please justify why not.

Treatment is standard of care.

12. In case of international research (research outside of the U.S. or research on international populations (non-U.S.)), describe qualifications/preparations that enable you to evaluate cultural appropriateness and estimate/minimize risks to subjects. Include whether research is sensitive given cultural norms.

a. State any local laws/regulations governing Human Subjects Research in the country(ies) you will conduct the research and attach any relevant approvals. If none, state N/A.

b. Will there be language barriers and if so, how will they be addressed?

Note: If materials are to be distributed to subjects in their native language, please follow SLU's Guidance For Studies Involving Non-English Speaking Subjects.

NOTE: Export control laws include the transfer of technical information and data, as well as information and technology to foreign nationals. If this study has international components, contact the SLU Export Control Officer for direction on whether export control policies apply.

* * * Benefits/Alternatives, Procedures to Maintain Confidentiality and Privacy * * *

10. Benefits/Alternatives

a) Benefits. Describe the potential benefit(s) to be gained by the subjects and how the results of the study may benefit future subjects and/or society in general. Indicate if there is no direct benefit to the participants.

Patients may or may not benefit from this study. Future patients with vestibular migraines may benefit from the knowledge obtained from this study.

Protocol Title: A Prospective randomized cross-over trial of nortriptyline and topiramate in the initial treatment of vestibular migraine

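### Beyond ten prompted symptoms and the C-SSRS, the plan gives no systematic way to elicit, record or pool adverse events, and it plans no safety analysis

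*Combined protocol and SAP*

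**What the plan says.** Section 3b makes a general promise, "Adverse effects of the two drugs will be assessed", and follows it with the only stated collection rule: "Specifically, the following known side effects will be asked about and recorded". The two lists are "Nortriptyline: somnolence, weight gain, dry mouth, blurred vision" and "Topiramate: Weight loss, parasthesias, forgetfulness, nausea, diarrhea, fatigue". Section 3b also schedules the C-SSRS at entry and at follow-up contacts, and Section 9.9 confirms it for each appointment.

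Section 9.3 describes a wider set of risks. For topiramate it gives "paresthesia (35-50%) and taste perversion (10-15" (both ranges are percentages). It then names warnings that include "Oligohidrosis and Hyperthermia, Metabolic Acidosis, Suicidal Behavior and Ideation" and kidney stones, and adds further effects from a package-insert table with an incidence of 2-5%. The nortriptyline account begins "Cardiovascular - Hypotension, hypertension, tachycardia, palpitation, myocardial infarction", continues to arrhythmias, heart block and stroke, and later names serotonin syndrome.

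Section 9.11a answers no to a monitoring board. Section 9.11b reads "Is there a Data Safety Monitoring Plan (DSMP)? N". The reason given for both is that the treatment is standard of care. Section 3d covers patient-reported effectiveness/acceptability, MSQ, DHI, the three subtypes and the crossover comparison of DHI. It does not mention adverse events.

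**The concern.** The prompts do not follow the plan's own risk figures. One effect that the plan regards as common in topiramate users has no prompt, while several that it regards as less common do. Most of the serious risks are also left to whatever a patient happens to volunteer.

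This matters because acceptability is part of the outcome on which the trial is powered. A comparison of two drugs on acceptability needs harms data gathered in the same way in both groups. Events that surface only in ordinary care depend on what the patient mentions and what the clinician writes down. With no pooled review and no planned tabulation, nobody is assigned to compare the drugs on harms, either during the trial or at its end.

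**Working it through.** **1. The plan's own figure.** Section 3b assumes 45 per group, 60% versus 30%, and a pooled Z-test at alpha 0.05 (read as two-sided). Mean proportion = 0.45. Null SE = sqrt(2 × 0.45 × 0.55 / 45) = 0.1049. Alternative SE = sqrt((0.24 + 0.21) / 45) = 0.100. Power = Φ((0.30 − 1.96 × 0.1049) / 0.100) = Φ(0.944) = 0.8275, against the stated 82%. The figure reproduces and is not in dispute. It supplies the 45 used below.

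**2. Prompts counted.** 4 (nortriptyline) + 6 (topiramate) = 10.

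**3. Section 9.3 set against the collection provisions.**

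| Risk named in Section 9.3 | Prompt in 3b | Other provision in the text |
|---|---|---|
| Taste perversion (topiramate, 10-15%) | None | None specific |
| Paresthesia (topiramate, 35-50%) | Yes | – |
| Nausea, diarrhea, fatigue, weight loss (topiramate, 2-5% table) | Yes | – |
| Suicidality (both drugs) | None | C-SSRS |
| Cognitive effects and fatigue (topiramate) | Partly: forgetfulness, fatigue | – |
| Acute myopia / angle closure (topiramate) | Blurred vision, listed under nortriptyline only | Watch item tied to weaning |
| Kidney stones (topiramate) | None | None specific |
| Cardiovascular effects, serotonin syndrome (nortriptyline) | None | None specific |

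**4. Size of the taste gap.** Expected cases = n × rate.

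- 45 randomised to topiramate: 45 × 0.10 = 4.5; 45 × 0.15 = 6.75.
- Upper limit if all 90 took topiramate at some point (crossover is optional): 90 × 0.10 = 9; 90 × 0.15 = 13.5.
- Chance of at least one case in 45 at the lower rate: 1 − 0.90^45 = 0.991.
- For contrast, an effect from the 2-5% table, which is prompted: 45 × 0.02 = 0.9; 45 × 0.05 = 2.25.
- If flexible dosing cut the taste rate to 5% (an assumption): 45 × 0.05 = 2.25 cases, and the chance of at least one is 1 − 0.95^45 = 0.90.

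**5. What full capture of serious events could show.** The documents give no rates for these. With zero events in n patients, the one-sided 95% upper bound is 1 − 0.05^(1/n): 6.4% for n = 45 and 3.3% for n = 90. At an assumed true rate of 1%, the chance of seeing at least one event is 1 − 0.99^45 = 36% or 1 − 0.99^90 = 60%.

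**6. Same questions for both drugs?** Section 3b does not say whether each list goes only to users of that drug. Somnolence, for example, is prompted under nortriptyline, while Section 9.3 also gives it for topiramate. A tabulation by drug needs identical questions in both groups.

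**The case against.** A reader might infer that collection is confined to the ten symptoms and that everything else goes unrecorded and unreviewed. The documents do not support that. The general sentence in 3b promises assessment of adverse effects, and the list that follows names prompts without ruling out other entries. Contacts include a history. Section 3c describes close physician contact, Section 9.9 provides a clinician to evaluate and treat or refer for any reaction, and 3b places all patient data in the electronic health record. Section 16 lists a follow-up phone script and questionnaires that were not available for review and may hold further prompts.

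Two other strong readings also fail. Tallying the topiramate warnings that lack a prompt would overstate the gap: angle closure has a watch item at weaning, blurred vision may pick up some eye events, and metabolic acidosis and hyperammonemia are laboratory findings. Nor does the answer in 3c show a missing safety rule, because that question asks about early decisions on efficacy.

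It is also fair to say that the form allows for no monitoring plan where risk is low, that both drugs are marketed, that patients can reflect an unpleasant taste in their acceptability rating, and that a trial this small cannot compare rare serious risks.

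What remains is that individual care is not systematic collection. Contacts may be by phone, and a switch for intolerance may be made by a call to the pharmacy without a visit. A health record stores what is entered but does not elicit it. Calling the treatment standard of care does not say how a randomised comparison will record harms. Even a good phone script would not supply the missing pooled review or the missing analysis.

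**Conclusion.** The point holds in a limited form. The stated prompts miss an effect that the plan itself puts at 10-15% (about 4.5 to 6.8 cases in 45 patients) and most of the serious risks that it names. No aggregate review or adverse-event analysis is planned. The likely result is incomplete harms data gathered unevenly, in a comparison powered on effectiveness/acceptability. Power and sample size are unaffected.

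The case count assumes that the Section 9.3 rate applies to patients who adjust their own dose towards the lowest effective one; a lower true rate shrinks it in proportion. The statement about elicitation rests on the available text, since the phone script could add prompts. The absence of a monitoring plan and of a safety analysis does not depend on that script. The change is worth making, but the point does not invalidate the design.

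**What to change.** - **Section 3b:** keep the ten items and add taste change. At every existing contact, add one open question on any new health problem, emergency visit or hospital stay since the last contact. Put the questions to all patients, whichever drug they take. Record onset date, current drug and seriousness for each event.
- **Section 9.11b:** replace the N with a brief plan. A physician already on the team reviews each serious event when it is reported, and reviews pooled events by drug at a fixed interval, for example quarterly.
- **Section 3d:** add a table of adverse events by drug.
- **Phone script:** check that it carries the same questions.

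The cost is a protocol amendment, slightly longer contacts and a short periodic review by existing staff. One limit remains: an open question will not detect laboratory abnormalities that cause no symptoms.

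### Solicited side effects sit in two drug-specific lists with no shared item and no visual item for topiramate; one common checklist would make recording comparable (minor)

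*Combined protocol and SAP*

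**What the plan says.** Item 3b (Study Procedures) opens with a general statement, "Adverse effects of the two drugs will be assessed", and then becomes specific: "Specifically, the following known side effects will be asked about and recorded". Two lists follow, each under a drug name:

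- "Nortriptyline: somnolence, weight gain, dry mouth, blurred vision"
- "Topiramate: Weight loss, parasthesias, forgetfulness, nausea, diarrhea, fatigue"

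The text does not say whether a patient is asked one list or both.

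Item 9.3 (Risks) gives the longer reaction lists. Those for topiramate include "Acute Myopia and Secondary Angle Closure Glaucoma, Visual Field Defects, Oligohidrosis and Hyperthermia, Metabolic Acidosis", with no restriction to the period of stopping the drug. Item 8h excludes patients with glaucoma and gives topiramate as the reason.

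Contacts at two, three and four months on drug may be in clinic or by phone (item 3b). Patients may take both drugs in turn. The analysis plan in item 3d names no comparison of adverse events.

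**The concern.** This is an open-label comparison of two drugs whose side effects overlap. An effect that is asked about on one drug and left to spontaneous report on the other will tend to be recorded more often where it is asked. A later table of side effects by drug would then partly reflect the questioning. That matters for any informal reading of tolerability, even though no formal test is planned.

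Vision is the clearest case. Blurred vision is asked about under nortriptyline. The protocol's own risk list names serious eye reactions under topiramate, and the eligibility criteria act on that risk, but the topiramate list has no visual prompt.

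Because a patient may move from one drug to the other, a complaint recorded without an onset date is also hard to assign to a drug.

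**Working it through.** The plan gives no figure on this point, so the check is a comparison of the lists in item 3b with the reactions in item 9.3.

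**Step 1. Visual items solicited (item 3b).** Nortriptyline 1 of 4 (blurred vision). Topiramate 0 of 6.

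**Step 2. Visual reactions listed (item 9.3).** Nortriptyline 3: blurred vision, disturbed accommodation, mydriasis. Topiramate 2: acute myopia with secondary angle-closure glaucoma, and visual field defects.

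**Step 3. Overlap.** Each of the 4 + 6 = 10 solicited items against the item 9.3 text for the other drug:

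| Item | Solicited under | Also listed in 9.3 for the other drug? |
|---|---|---|
| Somnolence | nortriptyline | yes |
| Weight gain | nortriptyline | no |
| Dry mouth | nortriptyline | no |
| Blurred vision | nortriptyline | not in those words (two other eye reactions) |
| Weight loss | topiramate | yes |
| Paresthesias | topiramate | yes |
| Forgetfulness | topiramate | no |
| Nausea | topiramate | yes |
| Diarrhea | topiramate | yes |
| Fatigue | topiramate | no |

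Items on both item 3b lists: 0 of 10. Items the protocol names for both drugs: 5 of 10. Somnolence is the weakest of the five, because item 9.3 pairs it with fatigue for topiramate and fatigue is solicited there. Without it the count is 4 of 10.

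**Step 4. What each reading leaves out.**

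- *List asked by current drug.* The five shared effects are each solicited on one drug only, and vision is asked about on nortriptyline but not on topiramate.
- *Both lists asked of everyone.* All ten items reach all patients, blurred vision included. Only eye pain is not asked about.

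**Step 5. Added questions per contact under a common checklist.** Checklist length = 10 + 1 = 11.

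- Both lists already asked of all: 11 − 10 = 1 more.
- By current drug: 11 − 6 = 5 more on topiramate, and 11 − 4 = 7 more on nortriptyline.

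If the new visual question replaces blurred vision instead of standing beside it, each figure falls by one.

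**Step 6. Link to the sample size.** Item 3b's power statement uses 45 per group and 60% against 30% for patient-reported effectiveness/acceptability. The pooled rate is 0.45, so the standard error is √(2 × 0.45 × 0.55 / 45) = 0.1049 under the null and √((0.24 + 0.21) / 45) = 0.1000 under the alternative. Power = Φ((0.30 − 1.96 × 0.1049) / 0.1000) = Φ(0.944) = 82.8%, against the stated 82%. No side-effect count enters this calculation.

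**The case against.** The strongest reply is that no defect is shown. Item 3b places no limit on who is asked, and the drug names may only label where each known effect comes from. On that reading blurred vision already reaches topiramate patients. The opening sentence is general, each contact includes a history, item 3c promises close contact with a physician, and item 9.9 promises evaluation, treatment or referral for any adverse reaction. Glaucoma is excluded at entry. A short list of common effects plus open history is a legitimate design. The phone script, questionnaires and consent form, which are listed but not reproduced, may settle what is asked. Item 3d plans no adverse-event comparison, so no planned test is biased.

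Most of this stands, and it keeps the point minor. Two things remain. The rule for who is asked what is not stated in the text available, and it decides whether five shared effects are recorded on a like-for-like basis. The general assurances name no visual symptom.

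A reader might also infer that the study watches for the glaucoma event only while topiramate is being stopped. Item 9.3 says "Patients will be asked to wean off of drug over the course of one week" and continues "Specific issues we will watch for include", and the topiramate entry there concerns acute withdrawal. The documents do not support that inference. The item 9.3 form prompt asks for adverse effects of washout periods, and this paragraph answers it. Its list is not worded as complete, and on-treatment precautions belong to item 9.9. The paragraph says nothing about what is watched during treatment, so no share of treatment time under watch can be derived from it.

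**Conclusion.** The point holds as a cheap, minor improvement. The facts that carry it are counts from the text: no shared item among ten solicited, five of the ten named for both drugs, and no visual item among the six for topiramate despite two listed eye reactions.

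The consequence depends on an unstated rule. Asking by current drug is the natural reading, because the lists are headed by drug, but it is not certain. Under it, elicitation is unequal and topiramate patients have no visual prompt. Under the other reading only eye pain is missing.

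Two stronger conclusions are tempting. One is that patients are in fact questioned unequally; the text does not settle this, and the forms that might could not be seen. The other is that the trial has a safety defect; the general follow-up and referral text, the glaucoma exclusion and the unseen forms rule out saying so. No event rate or detection rate is claimed. The primary comparison, sample size and power are unaffected.

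**What to change.** In item 3b, state that one common checklist is put to every patient at every existing contact, whatever the current drug. It consists of both present lists together plus *new blurred or changed vision, or eye pain*. For each positive answer, record the onset date, so that it can be placed against drug start, dose change and stop. If the attached forms already work this way, a sentence in item 3b saying so is enough, with the eye-pain wording added where it is missing.

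**Cost.** A wording change in item 3b and in any form that repeats it. One more question per contact if both lists are already asked of all; otherwise about 5 more on topiramate and 7 more on nortriptyline, plus a date for each positive answer. No added visit, test or patient.

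**Limits.** Some positive visual answers will be migraine aura, which is common ground with the disease under study. The history in item 3b already covers visual scotoma and gives a baseline for sorting these out. A question at scheduled contacts is a weak detector of an acute event between them. The clinical response to a positive answer stays with the investigator.
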